### Chapter 3: Study Design

This proposed experiment is an ancillary study of a multi-center, randomized clinical trial Bifocal Lenses In Nearsighted Kids (BLINK) Study (U10EY023208), which compares myopia progression rate between subjects wearing single vision contact lenses and those wearing soft bifocal contact lenses. The BLINK Study will enroll 294 myopic children aged 7 to 11 years at two clinical centers: The Ohio State University (OSU) College of Optometry and The University of Houston College of Optometry (UHCO).

The subjects in the BLINK Study will be randomly assigned to wear either single vision soft contact lenses or soft bifocal contact lenses with either a +1.50 D add or +2.50 D add power for at least three years, with 49 subjects in each treatment arm at each clinical center. This proposed study will recruit one group of 52 additional subjects that meet BLINK eligibility criteria and that are age-matched with a comparison group -- 49 BLINK study participants who are wearing soft bifocal contact lenses with +2.50 D add power.

The subjects in this proposed study will wear soft bifocal contact lenses in combination with daily administration of 0.01% atropine for three years. The rates of myopia progression and axial elongation will be compared to those in the comparison group in the BLINK Study. The protocol for the outcome measures in this proposed project is consistent with the BLINK Study.

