To test these hypotheses, I will enroll 52 myopic children aged 7 to 11 years into a treatment protocol of wearing soft bifocal contact lenses in combination with daily administration of one drop of 0.01% atropine for three years. The rates of myopia progression and axial elongation will be compared to the rates in age-matched subjects who are receiving treatment with only soft bifocal contact lenses in the Bifocal Lenses In Nearsighted Kids (BLINK) Study (U10EY023208). The BLINK Study is a multi-center, randomized clinical trial chaired by my primary mentor, and it was designed to test the hypothesis that the peripheral myopic defocus produced by the add power of soft bifocal contact lenses is responsible for slowing myopic eye growth.

**Aim 1. To test whether the combined treatment of 0.01% atropine and soft bifocal contact lens wear produces slower myopia progression and axial elongation compared to soft bifocal contact lenses alone over 3 years.** I will compare the three-year change in spherical equivalent refractive error and axial length of subjects undergoing the combined treatment to age-matched subjects wearing only soft bifocal contact lenses in the BLINK Study.

**Aim 2. To test whether early changes in choroidal thickness can be used as predictors of long-term myopia progression / axial elongation.** I will measure the change in choroidal thickness from baseline to 3 weeks in the subjects receiving combination treatment and in the BLINK Study subjects using soft bifocal contact lenses alone. I will then determine whether the amount of 3-week change in choroidal thickness correlates with the 3-year rate of myopia progression / axial elongation in each group.

**Scientific & Clinical Impact:** The results of this study will have significant implications for future studies to develop and test new therapeutic regimes that optimize the effect of myopia control through combined pharmacological and optical interventions. The outcomes will also aid in understanding the potential role of short-term changes of choroidal thickness in long-term regulation of myopia progression and ocular growth.

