## Chapter 4: Statistical Analysis Plan

The sample size calculations for all Specific Aims were performed using PASS 2005 (Hintze J, 2007) software using  $\alpha = 0.05$  and  $\beta = 0.20$  (power =80%) and then combined to determine the optimal sample size to address all of the aims. Estimates of sample size were computed for each specific aim, as follows:

**Specific Aim 1:** To test whether the combined treatment of 0.01% atropine and soft bifocal contact lens wear produces slower myopia progression and axial elongation compared to soft bifocal contact lenses alone over 3 years.

For Aim 1, the sample size is driven by the desired difference in spherical equivalent progression between the two groups. This difference needs to be of a magnitude that is considered clinically relevant. [name] and colleagues showed that the mean ( $\pm$  SD) myopia progression of single vision soft contact lens wearers was  $-1.29 \text{ D} \pm 0.71$  over three years ([name] et al. 2008). The proposed myopia progression in the +2.50 D add soft bifocal group for the sample size calculation of the BLINK Study based on a treatment effect of 50% was  $-0.65 \text{ D}$ . A reasonable reduction in myopia progression from the addition of atropine to the +2.50 D add bifocal lenses would be about  $0.33 \text{ D}$ , an additional reduction of 50%. Using a standard deviation of  $0.71 \text{ D}$  and taking into account the pair-matched design, the sample size for this aim would be 39 subjects per group.

**Specific Aim 2:** To test whether early changes in choroidal thickness can be used as predictors of long-term myopia progression / axial elongation.

For Aim 2, the correlation between choroidal thickness and refractive error / axial length ranges from 0.35 to 0.74 based on previous studies (Nishida et al. 2012; Flores-Moreno et al. 2013; Vincent et al. 2013). A sample size of 44 per group will allow for detecting a correlation of 0.41 between short-term changes in choroidal thickness and long-term myopia progression / axial elongation.

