## Chapter 5: Eligibility

In order to participate in the study, all subjects must meet the following criteria at Visit 1:

Age at baseline examination	7 to 11 years of age, inclusive
Spherical component of refraction	-0.75 to -5.00 D in each eye, inclusive, cycloplegic autorefraction
Astigmatism	≤1.00 DC in each eye, cycloplegic autorefraction
Anisometropia	≤2.00 D, based on spherical component
Best-corrected visual acuity (VA)	+0.1 logMAR or better in each eye at distance
VA with bifocal contact lens	+0.1 logMAR or better OU with +2.50 D add bifocal contact lenses at distance and near
Contact lens fit	The +2.50 D add soft bifocal contact lens must provide adequate movement and centration for continual wear
Compliance with atropine	Finish at least 85% of 0.01% atropine during the run-in period (see description in text)
History of vision correction	By patient report, not more than one month of gas permeable, soft bifocal, or corneal reshaping contact lens wear.
Myopia control	By patient report, not more than one month of participation in myopia control with treatments including, but not limited to, soft bifocal or orthokeratology contact lenses, atropine, bifocal spectacles
Ocular health	No eye diseases or binocular vision problems that may affect vision or contact lens wear (e.g. strabismus, amblyopia, etc.)
Ocular surgery	No previous intraocular or corneal surgery
Systemic health	No systemic diseases that may affect vision, vision development, or contact lens wear (e.g. diabetes, Down's syndrome, etc.)
Medications	No chronic use of medications that may affect immunity, such as topical or systemic use of corticosteroids
Participation	Agree to participate in the study for three years

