For participants who meet the above eligibility criteria except “compliance with atropine” at the baseline visit, we will schedule a 1-week follow-up visit for atropine dispensing as well as contact lens insertion, removal, and care training. At the 1-week Visit, we will prescribe a 2-week supply of 0.01% atropine and give instructions on how to use the eye drops and the side effects of atropine. The participants will be asked to use atropine for 2 weeks (**run-in period**) and then return to clinic to determine final eligibility. We will weigh the atropine with its bottle before giving it to the participant, and ask the participants to bring the remaining atropine to the clinic at the 3-week Visit. We will weigh the remaining atropine with its bottle, and subjects who finish at least 71% of the atropine eye drops based on the weight during the run-in period (missing drops no more than 2 days per week on average) will be eventually enrolled in the study.

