## Chapter 6: Outcome Measures

There are nine scheduled visits during the BAM Study. Outcome measures are completed at every visit, but the primary outcome measures will be conducted at the baseline and annual visits. Visits are listed by number in Table 6-1.

Table 6-1: Visit numbers and timing of the visit.

Visit Number	Timing
1	Baseline
2	1 week
3	3 weeks
4, 6, 8	6, 18, and 30 month visits
5, 7, 9	1, 2, and 3 year visits

Procedures performed at each visit are noted in Table 6-2.

Table 6-2: Schedule of measurements for the study. Cycloplegic autorefraction is the primary outcome.

	Visit 1	Visit 2	Visit 3	Visits 4, 6, 8	Visits 5, 7, 9
Manifest refraction (OU)	X				
Spherical over-refraction (OU)			X	X	X
High contrast VA (OU) OD/OS at baseline	X (M)		X (CL)	X (CL)	X (CL)
Low contrast visual acuity (OU)	X (M)		X (CL)	X (CL)	X (CL)
Near visual acuity (OU)	X (M)		X (CL)	X (CL)	X (CL)
Modified Thorington	X (M)		X (CL)		X (CL)
Acc lag and peripheral defocus with CL, near (OD)			X		X
Contact lens centration, movement (OU)	X	X	X	X	X
Choroidal thickness (OD)		X	X		X
Slit lamp examination (OU, no contact lens)	X	X	X	X	X
Pupil size (OD)	X		X	X	X
Non-cycloplegic autorefraction (OU)	X			X	X
Manifest refraction (OU)					X
Accommodative Lag with Manifest (OD)	X				
Cycloplegic autorefraction (1° outcome, OU)*	X				X
Peripheral refractive error without CL (OD)*	X				X
Axial length (OU)*	X				X
Peripheral eye length (OD)*	X				X
Videophakometry*	X				X
Peripheral defocus with CL (OD)*	X				X
Intraocular pressure (OU)*	X		X	X	X
Dilated fundus examination (OU)*	X				X
Contact Information Form	X				X
History Form	X				
Myopia Risk Factor Form	X				X
CISS Form	X		X	Visit 4 only	X
Contact Lens Form			X	X	X
Atropine Side Effect Survey	X		X	X	X
Compliance Forms (Contact Lens & Atropine)			X	X	X
Insertion, Removal, and Care Training		X			
Approximate Length of visit (hours)	2.5 to 3.0	1.0 to 1.5	1.0 to 1.5	1.0	2.5 to 3.0

CL = contact lens; M= Manifest refraction; \* = cycloplegic; Acc = accommodative

At Visit 1, we will measure high contrast distance visual acuity with the manifest refraction to determine eligibility. We will also measure low contrast and near visual acuities with the manifest refraction to determine the subjects' best

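### Aim 1 is a non-randomised comparison whose only named control for baseline differences, beyond shared eligibility, is age matching; no analysis, pairing rule or baseline adjustment is declared

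*Combined protocol and SAP*

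**What the plan says.** **Design.** Chapter 3 states: "This proposed study will recruit one group of 52 additional subjects that meet BLINK eligibility criteria and that are age-matched with a comparison group". That comparison group is 49 BLINK children wearing the +2.50 D add lens. BLINK randomises at two centres, "with 49 subjects in each treatment arm at each clinical center", but there is no randomisation between BLINK and this study. Chapter 3 adds that outcome measurement follows the BLINK protocol.

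**Comparison.** Chapter 2, Aim 1: "I will compare the three-year change in spherical equivalent refractive error and axial length of subjects undergoing the combined treatment to age-matched subjects" in BLINK. The paragraph before it says: "The rates of myopia progression and axial elongation will be compared to the rates in age-matched subjects".

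**Analysis.** Chapter 4 is titled Statistical Analysis Plan but holds only sample-size text. For Aim 1 it gives a 0.33 D difference, an SD of 0.71 D and, "taking into account the pair-matched design", 39 subjects per group. It names no test, model, covariate or pairing rule.

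**Eligibility.** Chapter 5 admits a spherical component of minus "0.75 to -5.00 D in each eye, inclusive, cycloplegic autorefraction". Children in this study also use atropine for a two-week run-in "and then return to clinic to determine final eligibility".

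**Data.** Chapter 6: "the primary outcome measures will be conducted at the baseline and annual visits". Table 6-2 marks cycloplegic autorefraction as primary and schedules axial length at the same visits. Near phoria and accommodative lag are also measured at Visit 1.

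**The concern.** Without randomisation, the group difference is the effect of atropine only if the groups have the same prognosis apart from treatment, or if the analysis corrects for where they differ. Age matching deals with age. It leaves baseline refraction, axial length, sex and any other predictor of progression free to differ between two studies recruited separately.

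Only a systematic difference matters here; chance imbalance is already reflected in the standard error. A systematic difference in a factor that predicts three-year change would move the estimate up or down, and a paired comparison matched on age alone would not remove it.

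Because the analysis is implied but not declared, the handling of pairs, unpaired children and covariates could be settled after outcomes are visible. Chapter 27 has the investigator and mentors propose analyses at meetings that also review intervention effects.

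**Working it through.** **1. The plan's figure.** Inputs from Chapter 4: difference 0.33 D, SD 0.71 D, alpha 0.05 (sidedness not stated), power 80%.

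- Paired, two-sided, normal approximation: n = (0.71 × (1.960 + 0.842) / 0.33)² = 36.3, so 37. With the noncentral t, power is 79.7% at 38 pairs and 80.7% at 39, so n = **39**. This matches exactly.
- Paired, one-sided t: 31.
- Unpaired, two-sided t: 74 per group.

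Of these variants, only the two-sided paired t-test gives 39, so a paired comparison is implied.

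**2. What that figure requires.** Chapter 4 cites 0.71 D as the SD of progression in single vision lens wearers, that is, in one group. The SD of a paired difference is 0.71 × √(2(1 − ρ)), which equals 0.71 only when ρ = 0.5. Power at 39 pairs is 81% at ρ = 0.5, 67% at ρ = 0.3 and 52% at ρ = 0. The documents state no ρ.

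**3. Pairing.** At most 49 of the 52 can be paired one to one. If both studies lose 18% (stated here; an assumption for BLINK), 52 × 0.82 = 42.6 and 49 × 0.82 = 40.2 remain. That leaves at most 40 complete pairs, and fewer if losses fall in different pairs. No rule covers this.

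**4. Size of a possible bias (illustration).** Let d be the systematic imbalance in SD units and R² the share of variance in three-year change that the factor explains beyond age. Bias = √R² × 0.71 × d. Neither d nor R² comes from the documents. False-positive rates are two-sided 5% with no true effect, 42 versus 40, SD 0.71 D.

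| R² | d | Bias (D) | Share of 0.33 D | False-positive rate |
|---|---|---|---|---|
| 0.05 | 0.1 | 0.016 | 5% | 5.1% |
| 0.10 | 0.3 | 0.067 | 20% | 7.1% |
| 0.20 | 0.5 | 0.159 | 48% | 17.0% |

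In the middle row a true 0.33 D would read as about 0.26 or 0.40 D, and a paired test with 40 pairs and SD of differences 0.71 D would have a 9.0% false-positive rate. In simulation of the middle row (20,000 data sets), about 7% of unadjusted tests rejected, and about 5% after regression on the factor. With d = 0 there was no inflation. The simulation assumes the factor is measured without error and acts linearly.

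**5. Power of an adjusted two-group analysis.** Residual SD = 0.71 × √(1 − R²), where R² is now the share explained by all covariates together; 42 versus 40; difference 0.33 D. Any loss from correlation between group and covariates is ignored.

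| R² | Power |
|---|---|
| 0 | 55% |
| 0.10 | 59% |
| 0.20 | 64% |
| 0.45 | 80% |
| 0.50 | 84% |

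**The case against.** **The analysis is not wholly open.** Chapter 2 fixes the endpoints and comparator, Table 6-2 names the primary outcome, and 39 reproduces as a paired t-test. A reader might infer from Chapter 4's silence that any analysis at all could be chosen. The documents do not support that: a paired comparison of three-year change is clearly implied. What stands is that it is not declared, has no pairing rule and would control age only.

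**The design has other safeguards.** Eligibility, lens add power and measurement protocol are shared. The 49 equals one BLINK arm at one centre, and Chapter 8 (Subject Selection) recruits from Columbus, so same-centre controls are plausible. This narrows the ways the groups can differ, but the centre is not stated, and a common protocol controls measurement rather than prognosis.

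**No systematic imbalance is shown.** This is correct. The refraction range applies to both groups, so it shows that imbalance is possible, not that it exists. The documents nowhere say that baseline refraction, axial length or sex predicts progression beyond age. The factors they do link to treatment effect, in spectacle studies, are near phoria (Chapter 10) and accommodative lag (Chapters 11 and 16). The selection difference the text does establish is the atropine run-in, which filters only the treated group and which adjustment cannot undo.

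**There is a route to prespecify.** Chapter 27 provides a meeting before study initiation to settle plans. It names no analysis, but it is a natural place to fix one.

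**Years 1 and 2.** A reader might infer that leaving the interim annual data out of Aim 1 is an error. It is not: three-year change is a legitimate endpoint, and a model using those data is a preference.

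**Conclusion.** The point holds in limited form. Aim 1 is a non-randomised comparison with age as the only named matching factor. Its implied paired analysis is undeclared, has no pairing rule and makes no baseline adjustment. If the two studies differ systematically in a prognostic factor other than age, the estimated effect of adding atropine is biased in an unknown direction.

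The size is unknown. The range of 0.016 to 0.159 D, with false-positive rates of 5.1% to 17.0% in the two-group test, rests entirely on assumed R² and imbalance; its top end needs both extremes together. A reader might infer that the trial's type I error is inflated to such a level. The documents do not support that, because they give no evidence of any imbalance, and with none there is no inflation.

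The case for change therefore rests on the fact that adjusting for baseline values already scheduled for collection is a better analysis for this design than pairing on age alone, and should be fixed before outcomes are compared.

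**What to change.** Before any comparison of outcomes, add to Chapter 4:

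- **Primary Aim 1 analysis:** regression of three-year change in spherical equivalent on group, adjusted for age, baseline spherical equivalent and sex. Add BLINK centre if both centres supply controls, and say which do. Run the same model separately for axial length with its own baseline.
- **Sensitivity set:** add baseline near phoria and accommodative lag, if the BLINK data include them.
- **Sensitivity analysis:** the age-paired comparison of three-year change, with its pairing rule and the handling of unpaired or incomplete pairs. Baseline-adjusted and change-score results can differ in non-randomised groups, so both should be reported.
- **Optional:** a mixed model that also uses years 1 and 2.

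**Cost.** No extra visits or subjects. It needs individual BLINK data: age, sex, and refraction and axial length at baseline and year 3. The analysis would depart from the paired sizing, and the SAP should say so together with its power. At about 42 versus 40 completers, power for 0.33 D is about 55% unadjusted and 59-64% if covariates explain 10-20% of variance; it reaches 80% only at about 45%. State alongside it that the paired plan's 80% depends on a within-pair correlation of 0.5 that is neither given nor justified.

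**Limitations to state.** Adjustment does not remove unmeasured confounding or selection by the run-in.

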### Sample Size Conclusion

Using the maximum required sample size (39 subjects for aim 1, and 44 for aim 2) and adjusting for 18% loss to follow-up gives a total sample required of **52**.

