### Reason for Measuring

[figure not shown]
Studies have reported changes in choroidal thickness in response to optical defocus. We will investigate whether changes in choroidal thickness occur over in the control and treatment groups. OCT images will be collected through a non-dilated pupil. Because choroidal thickness changes have been reported to occur rather quickly when the eye is exposed to a change in defocus, all choroidal thickness measurements will be made immediately after removing the child's study contact lens from the right eye. Measurements will be made at Visits 2, 3, 5, 7, and 9.

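### At the plan's own 18% loss neither Aim 2 group is expected to reach the stated 44 completers, and the plan does not say which BLINK children enter Aim 2

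*Combined protocol and SAP*

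**What the plan says.** Chapter 4, under Specific Aim 2, states: "A sample size of 44 per group will allow for detecting a correlation of 0.41" between the short-term choroidal change and long-term progression or elongation. The design values are alpha 0.05 and 80% power; sidedness is not given. The Sample Size Conclusion takes the larger of the two aims' sizes (39 and 44) and says that "adjusting for 18% loss to follow-up gives a total sample required of" 52. Chapters 2 and 3 make clear that 52 is the number of children recruited to the combination group.

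The lens-only children come from BLINK. Chapter 3 describes the comparison group as "49 BLINK study participants who are wearing soft bifocal contact lenses with +2.50 D add power", age-matched to the recruited children. It also says "The BLINK Study will enroll 294 myopic children aged 7 to 11 years at two clinical centers", randomised to single vision, +1.50 D add or +2.50 D add lenses, "with 49 subjects in each treatment arm at each clinical center". No loss allowance is stated for the 49, and no reason is given for that number.

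Chapter 2, Aim 2, does not mention 49. It refers to BLINK children using soft bifocal lenses alone, and asks whether the 3-week choroidal change correlates with 3-year progression or elongation within each group.

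**The concern.** A requirement of 44 per group is a requirement for analysable children, and the plan accepts this by inflating for loss. The inflation was applied only to the recruited group, and by multiplying by 1.18, which does not return 44 after an 18% loss. The lens-only group was fixed at 49 with no allowance shown. Aim 2 is tested separately in each group, so a surplus in one cannot offset a shortage in the other.

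At stake is a lens-only correlation with less power than the plan reports, while BLINK by design has twice as many wearers of the same lens. The plan's basis for 0.41 is also uncertain: the cited range of 0.35 to 0.74 concerns choroidal thickness against refractive error or axial length, and not a 3-week change against a 3-year change. A true correlation below 0.41 is quite possible, and there the extra children would matter more.

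**Working it through.** **Inputs.** Alpha 0.05, power 80%, r = 0.41 and 44 per group (Chapter 4). Loss of 18% and the recruited 52 (Sample Size Conclusion). Lens-only group of 49, and 49 per arm at each of two centres (Chapter 3). Assumption: the 18% also applies to BLINK children, for whom the documents give no rate.

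**1. The plan's figure.** Fisher z, two-sided: n = ((1.960 + 0.842)/atanh(0.41))² + 3 = (2.802/0.4356)² + 3 = 44.4. Exact bivariate-normal power is 79.6% at n = 43 and 80.6% at n = 44. So 44 reproduces with a two-sided test. A one-sided test needs 36 and does not reproduce it.

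**2. Inflation for loss.** 44 x 1.18 = 51.9, which gives the plan's 52. To have 44 left after 18% loss: 44/0.82 = 53.7, so 54.

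**3. Expected completers.**
- Lens-only: 49 x 0.82 = 40.2.
- Combination: 52 x 0.82 = 42.6.
- All BLINK +2.50 D wearers: 49 x 2 = 98 (check: 294/3 = 98); 98 x 0.82 = 80.4.

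**4. Power and detectable correlation.** Fisher z power = Φ(√(n − 3) x 0.4356 − 1.960). Detectable r = tanh(2.802/√(n − 3)).

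| Completers | Power at r = 0.41, Fisher z | Power at r = 0.41, exact | Detectable r at 80%, Fisher z | Power at r = 0.35, exact |
|---|---|---|---|---|
| 40 | 75.5% | 76.6% | 0.43 | 61% |
| 43 | 78.7% | 79.6% | 0.42 | 65% |
| 44 | 79.7% | 80.6% | 0.41 | 66% |
| 80 | 96.9% | 97.0% | 0.31 | 90% |

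**5. Chance of reaching 44 completers** (binomial, 82% retention): 10% from 49 and 39% from 52. The 49 would need a loss of no more than 1 − 44/49 = 10.2%; the 52 no more than 1 − 44/52 = 15.4%.

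**6. Sensitivity to the BLINK loss rate.** With no loss, 49 completers give 84.8% exact power. At 10.2% loss the group has 44 and 80.6%. At 18% it has about 40 and 76.6%.

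**The case against.** Several points on the other side are sound. The shortfall is small: about four power points in the lens-only group and about one in the combination group. The 18% is the plan's rate for its own recruits, and if BLINK loses no more than 10.2% the 49 are enough. Uncertainty about the true correlation outweighs a move from 0.41 to 0.43. A second centre is not free: a centre term removes a mean difference, but not unequal measurement error or a slope that differs by centre. Nor do the documents show that children at the Houston centre were scanned at Visits 2 and 3.

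Two stronger readings are tempting and should not be adopted.

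- A reader might infer that the plan restricts Aim 2 to one centre's 49 children. The Aim 2 text says neither. Chapter 3 introduces the 49 for comparing rates of progression and elongation, which is Aim 1. That they come from one centre is only suggested by the matching count. What stands is that no other lens-only group is defined, so the text needs clarifying.
- A reader might infer that Aim 2 is defective because it has no single vision reference. Aim 2 asks whether early choroidal change predicts progression within each treated group, and that can be tested without untreated children. Comparing +2.50 D with single vision wearers would be a new mechanistic objective. Chapter 14 does speak of whether "changes in choroidal thickness occur over in the control and treatment groups", but no Aim 2 analysis uses a single vision group. What stands is a limit on interpretation: a within-group correlation supports prediction, and does not show that the lens acts through the choroid.

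**Conclusion.** The concern holds in a limited form. The calculation behind 44 is correct for a two-sided test, but neither group is set up to deliver it at the plan's own loss rate: about 40 completers are expected in the lens-only group and about 43 in the combination group. The combination figure follows from the plan's numbers alone. The lens-only figure rests on two assumptions: that the 49 defined in Chapter 3 are the Aim 2 group, and that BLINK loses 18%. The effect on power is modest. The larger consequence is the gain forgone if scans exist for all 98 wearers: about 97% against 77% at r = 0.41, and about 90% against 61% at r = 0.35.

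**What to change.** 1. State in Chapters 2 to 4 which BLINK children enter Aim 2.
2. Where Visit 2 and Visit 3 choroidal scans exist, use all BLINK +2.50 D wearers at both centres for Aim 2, with a centre term, and report the slope by centre as a check. Keep the comparison group of 49 for Aim 1.
3. If those scans are not available, restate Aim 2 as about 40 lens-only and about 43 combination completers, with a detectable correlation of about 0.43 in the lens-only group.
4. In either case correct the combination figure, since a larger BLINK group does not help it. Either give about 43 expected completers, or note that 54 recruits would be needed for 44 (54 x 0.82 = 44.3).
5. Add a sentence that an Aim 2 correlation will be read as prediction. Using the single vision arm as an untreated reference is optional.

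The cost is a wider data request to BLINK and revised wording. Item 2 needs no extra enrolment, though a second centre's operators and scanner add some measurement variation. If this study has to process the extra images itself, the added work is 49 children x 2 visits x 6 sections = 588 b-scans.
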